## 2.2 Specific objectives:

## 2.2.1 The primary objective

Its purpose is to provide timely information on:

(i) Estimation of the cumulative incident risk (separately) of the following important identified risk for rivaroxaban users which is:

• Haemorrhage within gastrointestinal and urogenital organ sites (which meets the criteria for a major bleed) and all intracranial sites (Table 2))

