## 2.2.2 Secondary Objectives

These are given below. Their purpose is to provide timely information on:

Version 40 20/11/2014 REC Ref 12/SC/0592

(i) Prescriber and cohort accrual and the type of prescriber responsible for, and the setting of initiation of treatment with either rivaroxaban or alternative anticoagulant therapy.

(ii) Prevalence of non-clinical reasons for prescribing, prognostic health factors and clinical risk factors for haemorrhage as reported in medical charts for patients undergoing anticoagulation with either rivaroxaban or alternative anticoagulant therapy in the secondary care hospital setting and the treatment programme they received to advance the understanding of the patient population prescribed rivaroxaban in actual clinical practice in the secondary care hospital setting

(iii) Changes of health profile of patients, assessment of adherence, plus any alterations of the treatment programme during the 12 week observation period, as recorded in medical charts.(iv) To quantify the risk of:

(a) (separately) haemorrhage within gastrointestinal and urogenital organ sites (which meets the criteria for a major bleed) and all intracranial sites for contextual anticoagulant therapy cohort

(b) all major bleeding specified in primary objective for both rivaroxaban and contextual anticoagulant therapy cohort (as composite)

(c) (separately) haemorrhage (major bleeding according to Table 2) within critical organ sites other than specified in primary objective for both rivaroxaban and contextual anticoagulant therapy cohort

(d) all major and clinically relevant non-major bleeds (as a composite outcome)

(e) thromboembolic complications (incident and recurrent)

(f) other†† events including special outcomes of interest (severe hepatic failure and abnormal LFTs above 3x ULN) as recorded in medical charts during the 12 week observation period and, if number of reports are sufficient, in patient subgroups of special interest, including:

- reported indications
- elderly (>= 65 years)‡‡, other contraindicated or special groups (e.g. pregnant and breastfeeding women, patients with concurrent significant renal or hepatic impairment; patients with known VTE and/or haemorrhagic risk factors e.g. congenital or acquired bleeding disorders, uncontrolled severe arterial

<sup>†† Other than major and clinically relevant non major bleeding outcomes, or thromboembolic complications (recurrent or incident)

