## 4.2 Sample size

# 4.2.1 Sample size for primary outcome (haemorrhage – within intracranial, gastrointestinal and urogenital critical organ sites) where expected cumulative incidence is known

Where studies, such as clinical trials, have already estimated the impact of the exposure on the outcome of interest, the one objective of this observational study is to be able to estimate the measure of frequency so that it lies within a range (margin of error) close to the estimate from the RCT, assuming this represents the true value. Ideally this margin of error (also called precision) should be as narrow as possible, so that the frequency is estimated as precisely as possible [33], for example the margin of error is equal to half the width of the confidence interval. for the frequency estimate As such, in this study it is more appropriate to choose a sample size that will yield a confidence interval of a predefined width for those identified risks defined within the primary outcome which are of greatest clinical and medical importance i.e. major bleeding outcomes (Section 2.2.1). Table 3 displays the samples sizes (95% confidence intervals) across a range of expected incidences and levels of precision.

<sup>††† Overlap of data collection between SCEM and M-PEM should minimise any under-reporting of events of interest associated with the primary objective. However due consideration should be given to a) possible nonresponse of GPs for the long-term M-PEM study that might arise from the GP's knowledge that the patient is participating in the SCEM and b) that some patients are managed by specialist GPs purely on an outpatient basis and thus may never be officially admitted to hospital. The emphasis must be made that the two studies are complementary and participation in both is highly desirable.

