From rivaroxaban clinical trial data, the cumulative incidence of each of the primary outcome major bleeding events (GI, urogenital and intracranial) in patients taking rivaroxaban for DVT and prevention of recurrent DVT and PE over 12 weeks of treatment was approximately 0.2%, 0.1% and 0.0%, respectively. Since information on the reported incidence for intracranial major bleeding outcomes within the first 12 weeks of treatment is limited, the reported incidence of intracranial haemorrhage with enoxaparin/vitamin K antagonist (VKA) from RCTs of 0.1% within 12 weeks will be used as an estimate of the incidence of that event in this population for rivaroxaban. From clinical trial data, the cumulative incidence of the primary outcome major bleeding events was similar in patients taking rivaroxaban for PE (~0.3%). As such, we do not expect any difference in cumulative incidence of bleeding between PE and DVT patients.

The formula used to calculate the sample size based on an estimation of the proportion of patients who will experience major bleeding outcomes is[33]:

Sample size= 
$$3.84 \times p(1-p)$$
 \_where p= estimated proportion (cumulative incidence)  
(precision)

Thus in this population of patients taking rivaroxaban for the treatment of DVT and PE and prevention of recurrent DVT and PE, in order to estimate the expected (true) cumulative incidence of the primary outcomes of major bleeding (GI, urogenital and intracranial) of 0.4% (0.2%, 0.1% and 0.1%, respectively), within  $\pm 0.39\%$ , we would need a sample size of 1005 patients (Epi Info v6).

The cumulative incidence of each of the primary outcome major bleeding events (GI, urogenital and intracranial) in patients taking rivaroxaban for the prevention of stroke and systemic embolism in adult patients with non-valvular atrial fibrillation over 12 weeks of treatment was approximately 0.5%, 0.1% and 0.1%,‡‡‡ respectively. [5] Thus, in this population of patients taking rivaroxaban for the prevention of stroke and systemic embolism in adult patients with non-valvular atrial fibrillation, in order to estimate the expected (true) cumulative incidence of the primary outcomes of major bleeding (GI, urogenital and

<sup>‡‡‡ Approximate estimates of cumulative incidence in 12 weeks of treatment, based on steady increase in incidence over time and overall cumulative incidence from a median of 590 days treatment exposure (90/590\*N)

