intracranial) of 0.7% (0.5%, 0.1% and 0.1%, respectively), within  $\pm -$  0.69%, we would need a sample size of 561 patients.

Thus, in summary, for this study, a minimum sample size of 1700 evaluable patients for rivaroxaban is desirable to ensure the minimum of 1005 and 561 patients is achieved for each of the two indications described above for each drug, based on ratio of 1:2 respectively, with 12 weeks observation period sufficient to estimate cumulative incidence of specified primary outcomes of interest with desired precision. A similar number of evaluable new user alternative anticoagulant therapy patients will be collected for the internal contextual cohort.

In this study, sample size has been calculated such that the study estimate of cumulative incidence of major bleeding within each indication should fall with a pre-specified proportion which is relative to the true value. There is no ideal precision which should be used when calculating sample size, so use of proportion as an indicator of relative precision ensures the margin of error remains appropriate to the estimated size of cumulative incidence of major bleeding events.

Table 3. Sample sizes of evaluable patients required to estimate the expected (true)
cumulative incidence of a specified adverse event with 95% confidence intervals of
different precisions (0.2% to 5%).

Incidence	Precision							
from RCT	0.20%	0.39%	0.50%	0.69%	1%	2%	3%	5%
(%)								
0.10	958	252	153	81	38	10	4	2
0.20	1913	504	307	161	77	19	9	3
0.30	2864	755	459	241	115	29	13	5
0.40	3812	1005	612	321	153	38	17	6
0.50	4755	1255	764	401	191	48	21	8
0.70	6631	1752	1067	561	267	67	30	11
0.80	7564	2000	1218	640	305	76	34	12
1.00	9418	2494	1519	798	380	95	42	15
2.00	18475	4926	3003	1579	752	188	84	30
3.00	27187	7296	4452	2342	1117	279	124	45
4.00	35566	9605	5866	3089	1473	369	164	59
5.00	43627	11854	7246	3818	1821	456	203	73

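### The 1005 and 561 patients are derived from the three bleeding sites added together, a secondary outcome; for the separate primary sites, within indication, the relative precision the plan relies on is not reached.

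*Supplement*

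**What the plan says.** Section 2.2.1 sets the primary objective as "Estimation of the cumulative incident risk (separately) of the following important identified risk for rivaroxaban users", covering GI and urogenital major bleeds and all intracranial bleeds. Section 2.2.2 (iv)(b) makes the three together a secondary outcome: "all major bleeding specified in primary objective for both rivaroxaban and contextual anticoagulant therapy cohort (as composite").

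Section 4.2.1 is headed as the sample size for the primary outcome. For DVT/PE it enters a risk "of 0.4% (0.2%, 0.1% and 0.1%, respectively), within" ±0.39%, and obtains 1005. For AF it enters 0.7% (0.5%, 0.1% and 0.1%), within ±0.69%, and obtains 561. The total of 1700, split about 1:2 between AF and DVT/PE, is then described as "sufficient to estimate cumulative incidence of specified primary outcomes of interest with desired precision".

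The section explains its choice of precision in relative terms: the estimate within each indication "should fall with a pre-specified proportion which is relative to the true value", so that the margin stays in keeping with the size of the risk. It gives no numerical value for that proportion and no calculation for any site alone.

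**The concern.** The quantity sized is not the quantity named as primary. A sum of three risks is larger than each of its parts, and for rare events the relative margin widens as the risk falls. A size that just keeps the margin below the summed risk therefore cannot do so for each component.

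At stake is how the primary estimates will be read. Someone who takes the sufficiency sentence at face value will assume that each site-specific estimate has the relative precision described. For urogenital and intracranial bleeding, each indication is expected to yield about one event or fewer.

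**Working it through.** **Inputs, all from section 4.2.1.** The formula is n = 3.84 × p(1−p) / d². Here 3.84 = 1.96², which gives a 95% two-sided interval, and d is the half-width ("the margin of error is equal to half the width of the confidence interval"). Risks over 12 weeks are, for DVT/PE, GI 0.2%, urogenital 0.1%, intracranial 0.1%; for AF, 0.5%, 0.1%, 0.1%.

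**1. Reproduce the stated sizes.**
- DVT/PE: 3.84 × 0.004 × 0.996 / 0.0039² = 1005.8 (stated 1005).
- AF: 3.84 × 0.007 × 0.993 / 0.0069² = 560.6 (stated 561).

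Both reproduce, with the summed risk as p. Implied relative margins are 0.39/0.4 = 97.5% and 0.69/0.7 = 98.6%.

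**2. Absolute margin, one site at a time.** Table 3 gives the patients needed:
- at ±0.39%: 504 for a 0.2% risk and 252 for 0.1%, against 1005;
- at ±0.69%: 401 for 0.5% and 81 for 0.1%, against 561.

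Every site meets the absolute margins.

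**3. Relative margin, one site at a time.** Margin = √(3.84 × p(1−p) / n), compared with p:

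| Indication, n | Outcome | Risk | Margin | Margin / risk | Expected events |
|---|---|---|---|---|---|
| DVT/PE, 1005 | Composite | 0.4% | ±0.390% | 0.975 | 4.0 |
| | GI | 0.2% | ±0.276% | 1.38 | 2.0 |
| | Urogenital; intracranial | 0.1% each | ±0.195% | 1.95 | 1.0 each |
| AF, 561 | Composite | 0.7% | ±0.690% | 0.985 | 3.9 |
| | GI | 0.5% | ±0.584% | 1.17 | 2.8 |
| | Urogenital; intracranial | 0.1% each | ±0.262% | 2.6 | 0.6 each |

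With the full 1700 split 1133:567, the single-site ratios hardly move: 1.30 and 1.84 (DVT/PE), 1.16 and 2.60 (AF).

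**4. Chance of no event at a 0.1% site.** 0.999^1005 = 37% in DVT/PE; 0.999^561 = 57% in AF.

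**5. Indications pooled, n = 1700.** The GI risk is (567 × 0.5% + 1133 × 0.2%) / 1700 = 0.30%, with margin ±0.260%, or 0.87 times the risk. Each 0.1% site has margin ±0.150%, or 1.5 times the risk.

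**6. Exact intervals.** With so few events the normal approximation is poor: wherever the ratio exceeds 1, the lower limit falls below zero. Exact (Clopper-Pearson) 95% intervals are:

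| n | Events | Interval |
|---|---|---|
| 1005 | 0 | 0 to 0.37% |
| 1005 | 1 | 0.003 to 0.55% |
| 1005 | 2 | 0.02 to 0.72% |
| 561 | 0 | 0 to 0.66% |
| 561 | 1 | 0.005 to 0.99% |
| 561 | 3 | 0.11 to 1.55% |

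**The case against.** **The stated margins are absolute, and each site meets them.** This stands. A reader might infer that the planned precision is achieved for the composite alone; Table 3 contradicts that. In absolute terms the sufficiency sentence is true for every site. But section 4.2.1 explains the precision as relative to the risk, and the absolute figures mean little for a 0.1% site: ±0.39% reaches 0.49% and ±0.69% reaches 0.79%, about five and eight times the expected risk.

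**The relative target is inferred.** Also fair. The plan never states 97.5% or 98.6%, says there is no ideal precision, and phrases the target for major bleeding within an indication, which can be read as the sum. It does not promise that proportion for each site, so the shortfall is against its rationale, not against a numerical per-site criterion.

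**The primary estimate may pool the indications.** Section 2.2.1 speaks of rivaroxaban users, and section 4.7.2 lists indication as a stratum where possible. Pooled, the GI margin is below the risk, so it would be wrong to say that the margin exceeds the risk for every primary estimate. The 0.1% sites remain at 1.5 times, and section 4.2.1 itself sets the precision by indication.

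**Which quantity is primary is not uniform.** The executive summary describes the primary focus without saying that sites are separate, and lists quantification by organ site under the secondary focus. Sections 2.2.1 and 2.2.2 are explicit, so I follow them.

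**The report will carry confidence intervals anyway** (section 4.7.2). True, which limits the harm to what the protocol claims in advance.

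**Conclusion.** The concern holds in a limited form. The arithmetic of 1005 and 561 is correct; the mismatch is between the outcome sized (the composite, secondary) and the outcomes declared adequately sized (the separate sites, primary). Within indication, the 95% margin is 1.17 to 2.6 times the expected risk for every single site, against just under 1 for the composite. This is the size of the ratio itself; the excess over the risk is about 17% to 160%. Pooled over 1700, only the 0.1% sites exceed 1.

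These figures assume the plan's own expected risks, its normal-approximation formula and the minimum numbers per indication. The relative target is inferred from 0.39/0.4 and 0.69/0.7. The point should be corrected, but it does not call the design or the number of patients into question.

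**What to change.** Keep the sample size. In section 4.2.1:

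- State that ±0.39% and ±0.69%, and the relative precision they represent, were derived for the three-site composite, secondary objective (iv)(b).
- Limit the sufficiency sentence to that composite.
- Add the expected precision for each separate primary site, by indication and pooled, as exact intervals at plausible event counts; those in step 6 of the working can serve for the two indications.

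Align the executive summary with section 2.2.1 on whether the separate sites or their composite are primary.

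The cost is protocol wording only: no more patients and no change of analysis. The precision stated for the primary outcomes will look less favourable.

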# 4.2.2 Sample size for general safety surveillance of other events (aside from the primary outcome) where background rate is unknown.

For purposes of general safety surveillance (for events arising from exploratory objective (Section 2.2.3 (iii)) for the population of interest (i.e. those prescribed rivaroxaban according to labelled new indications), it is possible to estimate a sample size necessary to detect a minimum of three cases§§§ based on an assumed rate in that exposed sub-group and assuming the background rate is zero. [35] For this study, a sample size of at least 1700 evaluable patients (see section 4.3.2.3) should allow for the detection of at least three cases of an event if it occurs with a rate of at least one in 200, with 99% probability. [35]

## 4.3 Study Population

# 4.3.1 Phase 1: Selection of specialist HCP

Since it is known that managed entry of rivaroxaban into the NHS exists (to assist organisations in developing medicines management policies and to inform prescribing decisions) the accessible secondary care settings will be those for which recommendations for prescribing rivaroxaban have been adopted. Thus the actual secondary care hospital settings will be a subset of all secondary care hospital settings in England and Wales. A representative sample \*\*\*\*of specialist healthcare professionals responsible for prescribing anticoagulants ('specialist HCP') for medical conditions that require anticoagulation within those accessible settings will be systematically identified by the DSRU and will be invited to participate in the study prior to study start (anticipated May 2013, to be determined). This non-probability sampling method will be used because a probability sampling framework is not feasible as stated above.

Routes of identifying relevant specialist HCPs within these accessible settings will include the use of the existing clinical research networks and support networks provided by allied healthcare professionals, including hospital pharmacists, some of whom are highly specialised anticoagulation pharmacists working in secondary care hospital settings across England and Wales.

§§§ In many situations involving rare reactions it is assumed that the frequency of the event is small, so that the occurrence of the event follows a Poisson distribution and the 95% confidence interval (CI) calculated based on the number of events. If no events are observed in a study of X individuals then one can be 95% certain that the event occurs no more often that 3/X. [34]

\*\*\*\* Representativeness of specialist HCPs will be considered in terms of geography, secondary care setting (teaching, general, private, outpatient only).

Specialist HCPs will be informed that they will be participating in a cohort study which will monitor the extension of licence of a recently introduced oral antithrombotic agent (rivaroxaban), in accordance with requirements within the Risk Management Plan for that product. Using a bespoke website, specialist HCPs will be required to register online with the study co-ordinating centre (DSRU) in order to receive access to relevant study documentation. Each participating specialist HCP will be requested to make treatment decisions independent of the study and then to evaluate whether a patient is eligible for inclusion based on broad entry criteria (see below).

Remuneration, in line with the standard British Medical Association (BMA) rate will be paid to the NHS trust to cover time and administration costs incurred (either by specialist HCPs or associated staff) to assist with obtaining consent and completing questionnaires.

#### 4.3.2 Phase 2: Selection of patients

The accessible study population will be that portion of the target population of interest to whom participating specialist HCPs have access. The identification of the actual study population, (which will be a subset of the accessible study population) will be through (non-probability) systematic sampling whereby all consecutively identified†††† eligible new user patients treated by any specialist HCP (after the pharmacotherapeutic treatment decision has been made that one of the two study oral anticoagulants is the most appropriate treatment based on clinical need) and who provide consent ( see section 3.0) will be enrolled until the desired sample size is reached. This method will be used because a probability sampling framework is not feasible and because participation within the study is not required as a condition of receiving treatment. This approach is intended to reduce conscious or unconscious selection bias on the part of the specialist HCP as to whom to invite to participate in the study, especially with regard to prognostic factors that may be related to prognosis.

New users of rivaroxaban will be comprised of rivaroxaban naïve patients, who may or may not be antithrombotic or anticoagulant treatment naive patients newly initiated by specialist HCPs. The patient may then have medicines management transferred to the GP in primary care. Thus, the GP may take on the primary role of monitoring treatment, providing prescriptions and altering the dose when necessary, with the option of referral to secondary

<sup>†††† As relevant to the date that the specialist HCP registers to participate in the study

care if and when required. Alternatively, the patient may be primarily managed within the secondary care setting alone.

The contextual cohort will be comprised of patients for whom no exposure to anticoagulation therapy has occurred within the 12 months prior to initiation by the Specialist HCP for the current study. Clinical care pathway will be the same as that outlined above for rivaroxaban patients.

Since this is a new user inception or incidence rivaroxaban cohort that is being identified, this study avoids the introduction of a number of biases associated with existing users (including incidence/prevalence bias, survivorship bias, and follow-up bias) which may impact on the measure of frequency of primary objective. Data will also be available for the internal contextual cohort which will have been collected during the same calendar period, for similar indications using the same data collection methods, and all subject to the same protocol. This minimises effect of bias from non-random measurement error. However, whilst users of anticoagulant therapy appear to provide a 'logical' contextual cohort that may be similar with regard to some clinical risk factors, they may also differ with respect to other important confounding factors such as disease severity. The key purpose of this contextual cohort is to explore the variation in the distribution and determinants of prognostic and clinical risk factors. It is not to compare risk of primary outcome between the two groups.

The first part of the second phase of the study will involve participating specialist HCPs capturing (in anonymised format using patient unique identifier) brief summary data (e.g. sex, age, indication, bleeding/stroke risk score and non-clinical reasons for prescribing) as recorded in the medical charts for **all** individuals invited to participate (including those who declined) for whom the clinical decision to prescribe rivaroxaban or alternative anticoagulant therapy was made under conditions of real life practice. These data will help examine the representativeness of the study population.

Cohort recruitment will be examined regularly to monitor the number of evaluable patients included, so as to ensure that the desired ratio of 1:1 rivaroxaban: contextual cohort patients with the relevant indications is achieved in the final overall study cohort for secondary objective analysis.

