The aim of this Specialist Cohort Event Monitoring (SCEM) study is to monitor the shortterm (up to 12 weeks) safety profile and drug utilisation of rivaroxaban as prescribed to patients for medical conditions requiring anticoagulation by specialist HCPs in the secondary care hospital setting in England and Wales. A registry-based observational, population based cohort study with a contextual cohort, utilising the technique of cohort-event-monitoring will be used (section 4) for this purpose. In the three-year post approval period, the study aims to collect exposure and outcome data for a cohort of at least 1700 evaluable patients (each observed for a minimum of 12 weeks), comprising of a minimum of 561 and 1005 patients treated with rivaroxaban for the prevention of stroke and systemic embolism in adult patients with non-valvular AF (with one or more risk factors, such as congestive heart failure, hypertension, age  $\geq$  75 years, diabetes mellitus, prior stroke or transient ischaemic attack), and for the treatment of DVT and PE and prevention of recurrent thromboembolic events, respectively. In addition to the desire to study the use of rivaroxaban in a population that is more heterogeneous than those observed in clinical trials, it is desirable to put these observations into context. To characterise a population treated with existing anticoagulant therapy will allow the variation in determinants of treatment choices to be examined in relation to risk. Therefore, a similar number (at least 1700) of evaluable new user patients receiving alternative anticoagulant therapy will be recruited concurrently as an internal contextual cohort in order to characterise the adoption of rivaroxaban into clinical practice and explore possible differences in factors such as setting, prevalence of (non-clinical)\* reasons for prescribing, physician prescribing preference factors† and those clinical characteristics which are known risk factors for the primary outcomes of interest.[6] This study will not inform on relative measure of risk of primary outcome between rivaroxaban and the internal contextual cohort. The key purpose of this internal contextual cohort is to explore the variation in the distribution and determinants of prognostic and clinical risk factors. The purpose is not to compare risk of primary outcome between the rivaroxaban and the internal contextual cohort; a much larger study is required for that.

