regular review of the patient is needed. Note that knowledge of INR control is needed to assess the 'labile INR' criterion; otherwise for a non-warfarin patient, this scores zero.

In the UK, a NICE clinical guideline is available which outlines assessment of risks of VTE and bleeding in medical patients admitted to hospital. [29] It advocates a form of benefit risk assessment of offering VTE prophylaxis to medical, surgical and /or patients with trauma balanced against risk of VTE and bleeding. It also states that choice of pharmacological VTE prophylaxis should be based on local policy, clinical condition and patient preference. Thus it is important to examine whether the likely hierarchical clustering of patients –by region geographically and by medical institution has any impact on either bleeding risk assessment or incidence of haemorrhage.

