# 4.3.2.2 Patient Exclusion Criteria

Specific exclusion criterion for the alternative anticoagulant therapy cohort is:

- Any use of univalent direct thrombin inhibitor or direct factor Xa inhibitors.
- use of anticoagulant therapy or other vitamin K antagonists recorded within one year prior to index date.\*\*\*\*\*

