This relates to Section 2.2.1 secondary objective (v), the aim of which is to explore the effect of important predictors (prognostics characteristics, selected relevant risk factors and oral anticoagulant on the primary outcomes of interest (haemorrhage), **only if sufficient numbers of cases of primary outcome are reported**. The effect of physician anticoagulant prescribing preference factors (type of novel anticoagulants prescribed in previous calendar month; proportion of novel anticoagulant use of all anticoagulants prescribed in previous calendar month), medical education, setting and institution will be explored as a suitable conditioning (instrumental) variable for modelling..[40] Since, data are likely to be hierarchical the application of a multilevel model for discrete response data will be considered. Odds ratios and 95% confidence intervals will be calculated.

4.7.7 To describe clinical features and management of cases of overdose, major bleeding, VTE events indicating failure of anticoagulation and management of homeostasis in patients undertaking surgery (elective or urgent) reported in the first 12 weeks after treatment initiation in the cohort exposed to rivaroxaban.

The following relates to Section 2.2.3 exploratory objective (ii) . A qualitative assessment of these cases will include evaluation of patient demographic characteristics, treatment details, the detection and clinical features and management of events of interest, resolution, relevant investigations prior to and during therapy, the patient's relevant medical history and concurrent medication and any sequelae. Data will be derived from the SCEM and follow up questionnaires sent to gather other relevant essential information for construction of a case-series summary descriptive table.

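### Recent anticoagulant users may enter the rivaroxaban cohort but not the contextual cohort, so the between-cohort comparison of risk factors mixes an eligibility effect with channelling

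*Supplement*

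**What the plan says.** Section 4.3.2 defines the two cohorts differently. For one: "New users of rivaroxaban will be comprised of rivaroxaban naïve patients, who may or may not be antithrombotic or anticoagulant treatment naive patients". For the other: "The contextual cohort will be comprised of patients for whom no exposure to anticoagulation therapy has occurred within the 12 months prior to initiation". Section 4.3.2.2 repeats the one-year rule under the line "Specific exclusion criterion for the alternative anticoagulant therapy cohort is", and no matching rule is written for rivaroxaban.

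The Executive Summary and Section 4.3.2 give the main purpose of the contextual cohort as exploring how prognostic and clinical risk factors, and their determinants, are distributed. Section 4.7.3 presents index characteristics and prescribing reasons for each cohort. Section 4.7.6 is headed as a comparison of risk-factor prevalence between them. Neither restricts, stratifies or adjusts by earlier anticoagulant use. Section 4.7.5 does use naive and past-user groups, but for event risks and incidence densities.

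Several recorded items depend on earlier treatment. Section 4.4.2.2 lists labile INR, and non-adherence to or side effects of an earlier anticoagulant as reasons for prescribing. On the labile-INR item of HAS-BLED, Section 1.5 notes: "otherwise for a non-warfarin patient, this scores zero".

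Section 4.7.6 also proposes, if there are enough cases, to explore the effect of "selected relevant risk factors and oral anticoagulant on the primary outcomes of interest (haemorrhage"), with odds ratios. The Executive Summary states: "This study will not inform on relative measure of risk of primary outcome between rivaroxaban and the internal contextual cohort".

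**The concern.** A reader of the final tables will take a between-cohort difference in bleeding-risk profile as evidence on who is given rivaroxaban. Part of it will instead come from the entry rule. A rivaroxaban patient can arrive from a VKA with unstable INR. A contextual patient has been off anticoagulants for a year, so recent labile INR is largely excluded, and prescribing because a recent anticoagulant was not tolerated or not taken is much less likely.

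HAS-BLED has a further problem because Section 4.7.4 compares scores at index and at 12 weeks. At index the labile-INR item is open mainly to switchers in the rivaroxaban cohort. At 12 weeks it is open mainly to contextual patients then on a VKA. The score therefore changes meaning by cohort and by time.

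Section 5.2 foresees that patients who did badly on earlier treatment may be channelled to rivaroxaban, which is what the study wants to see. It does not mention the unequal washout, and Section 4.3.2 describes the cohort data as gathered under one protocol. The main secondary question is at stake, not the primary estimate.

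**Working it through.** **What the plan supplies.** The target is 1700 evaluable patients per cohort (Section 4.2.1). The underlying precision sizes reproduce: 3.84 × 0.004 × 0.996 / 0.0039² = 1005.8 (stated 1005), and 3.84 × 0.007 × 0.993 / 0.0069² = 560.6 (stated 561). They are not in dispute. The plan gives no effect size, test level or power for the between-cohort comparison, no expected share of switchers, and no factor prevalences. What follows is illustration under stated assumptions.

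**Set-up.** Let s be the share of rivaroxaban patients who used an anticoagulant in the previous 12 months, p0 a factor's prevalence in naive patients, and p1 its prevalence in switchers. Assume naive patients are identical in both cohorts, so there is no channelling among them. Then:

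- contextual prevalence = p0
- rivaroxaban prevalence = (1 − s) p0 + s p1
- difference due to eligibility alone = s (p1 − p0)

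**Results.** The ordinary factor has p0 = 10% and p1 = 20%. The VKA-dependent factor has p0 = 0% and p1 = 30%. The chance of significance is a normal approximation at 1700 per cohort, two-sided 5%.

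| s | Ordinary factor, rivaroxaban | Difference (points) | Odds ratio | Chance of significance | VKA-dependent difference (points) | Naive rivaroxaban patients left |
|---|---|---|---|---|---|---|
| 10% | 11% | 1.0 | 1.11 | 16% | 3 | 1530 |
| 20% | 12% | 2.0 | 1.23 | 46% | 6 | 1360 |
| 30% | 13% | 3.0 | 1.34 | 78% | 9 | 1190 |
| 50% | 15% | 5.0 | 1.59 | 99% | 15 | 850 |

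Worked line for s = 20%: 0.8 × 10% + 0.2 × 20% = 12%. SE = √[(0.12 × 0.88 + 0.10 × 0.90)/1700] = 0.0107, and 0.02/0.0107 = 1.86, so the chance of exceeding 1.96 is about 46%.

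With a weaker contrast (10% against 15%) the differences are 0.5, 1.0, 1.5 and 2.5 points, and the chances of significance 7%, 16%, 29% and 64%.

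**The 4.7.6 model, a separate matter.** Take two-thirds of 1700 as DVT/PE and one-third as AF, with the protocol's incidences: 1133 × 0.4% + 567 × 0.7% = 4.53 + 3.97 = 8.5 expected events. If the contextual cohort has the same, SE(log OR) = √(2/8.5) = 0.485 and the 95% interval is a factor of exp(1.96 × 0.485) = 2.6 either way. This width would be the same under identical entry rules, so it does not measure the washout problem. It does suggest that the condition of enough cases may not be met.

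**The case against.** The strongest reply is that moving a patient from a VKA to rivaroxaban is itself a prescribing decision, and describing uptake is an aim of the study. That stands. A reader might infer that the cohort differences are produced by eligibility instead of prescribing, but the documents do not support that. They show the two mixed and not separable in the planned comparison.

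Other tempting inferences also fail:

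- **That the new-user claim is false.** Section 4.3.2 says "Since this is a new user inception or incidence rivaroxaban cohort that is being identified, this study avoids the introduction of a number of biases", and goes on to tie these to existing users and to the primary frequency estimate. Switchers are new users of rivaroxaban, so the claim holds for rivaroxaban itself. Selection through earlier treatment with another drug remains.
- **That a drug odds ratio will be reported.** Section 4.7.6 makes the model conditional on enough cases, and considers an instrumental variable and a multilevel form. Neither of these two removes a cohort-specific entry rule.
- **That prior-therapy reasons cannot occur in contextual patients.** Section 4.4.2.2 sets no time limit, so use ending more than a year earlier could still be recorded.

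It is also fair that switchers are partly described: Section 4.7.3 mentions INR pattern in those switching, and Section 4.4.2.3 collects transition details. No separate analysis plan is shown, and table layout may be left to it. However, the protocol itself specifies naive and past-user groups for event rates, so the population for its main between-cohort comparison should be specified too.

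**Conclusion.** The point holds in limited form. The entry rules are explicitly unequal, and the comparison for which the contextual cohort was recruited does not account for them. Labile INR, HAS-BLED and prescribing reasons tied to earlier therapy will carry an eligibility component that cannot be told from channelling.

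Its size is unknown. The figures of 1-5 points for an ordinary factor and 3-15 points for a VKA-dependent one rest on an assumed 10-50% share of switchers across the whole rivaroxaban cohort and on assumed prevalences. If switching is confined to AF patients, about a third of the cohort, the whole-cohort share is about a third of the AF share, and the effect concentrates in AF. That is a reason to compare by indication.

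The cumulative incidence of haemorrhage on rivaroxaban is a single-cohort estimate and is unaffected. The change should be made before analysis, but the issue does not undermine the primary result. The wording of 4.7.6 conflicts with the Executive Summary and Section 4.3.2 regardless of the washout. It also cites a secondary objective (v), whereas Section 2.2.2 ends at (iv).

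**What to change.** **Main comparison.** In Sections 4.7.3 and 4.7.6, compare rivaroxaban patients who meet the same 12-month-naive rule with the contextual cohort, by indication. Show recent anticoagulant users on rivaroxaban as a separate group, so that switching stays visible. Prior anticoagulation is already collected (Sections 4.4.2.2 and 4.4.2.3), but no look-back date is stated for it. Confirm the date of last use, and state how anticoagulants given as acute care just before index are counted, identically in both cohorts.

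**HAS-BLED.** Also present the score without the labile-INR item for cohort comparisons and for index against 12 weeks.

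**Section 4.7.6 model.** Remove the drug term, or state that its odds ratio will not be read as relative risk between cohorts. Correct the objective reference.

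**Limitations.** Name the unequal washout in Section 5.2.

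**Cost.** Mainly analysis wording, plus a check on the date of last use. The naive subset would be about 850-1530 of 1700 at 50-10% switchers, so this comparison departs from 1:1. For a given prevalence its standard error grows by √[(1/(1 − s) + 1)/2], which is 1.03 at s = 10% and 1.22 at s = 50%. The full rivaroxaban cohort stays in the primary estimate.
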